## 2.2 BACKGROUND

ALS is a fatal neurodegenerative disorder characterized by progressive loss of motor neurons in the cortex, brain stem, and spinal cord. Relentless and progressive muscle atrophy and weakness are hallmarks of ALS. Most patients with ALS die from respiratory failure within 3 to 5 years after disease onset. Among the 3 Food and Drug Administration (FDA)-approved ALS treatments, riluzole and edaravone demonstrate only a moderate effect either on survival or functional decline, respectively, and more data is needed to further support the treatment effect of the recently approved treatment, the combination of sodium phenylbutyrate and taurursodiol. Therefore, there is still a significant unmet medical need for treating individuals with ALS.

SAR443820 has demonstrated strong RIPK1 inhibition with high potency in vitro in various cell types. Refer to the SAR443820 Investigator's Brochure (IB) for a detailed description of the chemistry, pharmacology, efficacy, and safety of SAR443820.

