3.2.1 Definition of endpoint(s)

Part A

The ALSFRS-R is composed of 12 items across 4 subdomains of bodily function (bulbar, fine motor, gross motor, and breathing), with each item scored on an ordinal scale from 0 (total loss of function) to 4 (no loss of function). The total score of the ALSFRS-R ranges from 0 to 48, with a higher score indicating better function (1). Good reliability between face-to-face and telephone administration of the ALSFRS-R has been demonstrated (2).

Part B

The survival endpoint will be defined as the time to death or permanent assisted ventilation (>22 hours a day for >7 consecutive days), whichever comes first. CAFS is used to compare each study participant's outcome to others in the trial in a series of pairwise comparisons, based on function and survival (3). For each pairwise comparison, a study participant is assigned a score and then the summed scores are ranked for all participants. To calculate a participant's CAFS, each participant is compared individually to all other participants in the trial. The summary score for each participant is the sum of the comparisons (+1, 0, -1) against all other participants. For each pairwise comparison of patients, the participant who fares better earns a point, and the one who fares worse loses a point. In the case of a tie, no points are added or subtracted. If both participants die, the one surviving longer fared better; if only one survives then that participant fared better; and if both participants survive, the one with the smaller decline in ALSFRS-R from baseline fared better. If a participant discontinues early, comparison to each other participant uses time to death if the comparator died; otherwise, the comparison is based on the last ALSFRS-R time-point available for both participants. Once these scores have been calculated for all subjects, they are ranked, from lowest (died first) to highest (best ALSFRS-R outcome among those who survived), yielding the final CAFS score used as the endpoint. The average rank score is then calculated for each treatment group. A higher mean rank score indicates that participants in that treatment group, on average, fared better.

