3.4.3 Comparison with external control

A matched analysis using data from historical clinical trial database (for example, PROACT) as a control will be conducted to demonstrate the superiority of SAR443820 on slowing down disease progression and prolonging survival over 104 weeks of treatment period.

Matching procedure

1. Pre-matching filtering: The participants in the historical clinical trial database will be filtered by the following factors that match our trial eligibility criteria and duration:
 - Age 18 – 80 years, inclusive
 - First ALS symptom onset ≤ 2 years
 - Baseline SVC (%) $\geq 60\%$
 - Baseline ALSFRS-R decline rate $\geq 0.5/\text{month}$
2. Propensity score matching: Propensity score matching seeks to balance the distributions of known prognostic covariates in treatment and control group to resemble what would occur had the treatment been randomly assigned. A logistic regression for the treatment group as the dependent variable is performed to obtain the propensity score with the abovementioned matching variables, using all the participants (planned for 174) randomized to the SAR443820 arm and the participants from the historical clinical trial database after filtering as described above. Each participant in the SAR443820 treated group will be matched 1:1 using the Mahalanobis distance to a participant in the historical clinical trial database. Matching will be performed with replacement.

To assess the success of the matching procedure, summary statistics of baseline matching variables will be presented and compared between the two treatment groups before and after matching to assess post-match balance.

Post-matching statistical analysis

Once the matching is performed, the comparison between participants who were randomized to SAR443820 and placebo arm generated from the historical trial database will be provided for the following endpoints using the similar analyses models as described for the primary and secondary endpoints in [Section 3.2.2](#) and [Section 3.3.1.2](#).

- Combined assessment of function and survival (CAFS) score at Week 52, Week 76, and Week 104
- Change from baseline in ALSFRS-R total score to Week 52, Week 76, and Week 104
- Time from baseline to the occurrence of either death or permanent assisted ventilation (>22 hour daily for >7 consecutive days) whichever comes first
- Time from baseline to the occurrence of death

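### SAP 3.4.3 sets no follow-up requirement for historical controls, so external-control CAFS is biased if a source trial planned less follow-up than the CAFS time point

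*SAP*

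**What the plan says.** SAP 3.4.3 plans a matched comparison of the SAR443820 arm with controls from a historical trial database, meant to show superiority on progression and survival over 104 weeks. The pre-matching step reads: "The participants in the historical clinical trial database will be filtered by the following factors that match our trial eligibility criteria and duration". Four factors follow. Two are "Age 18 – 80 years, inclusive" and "First ALS symptom onset ≤ 2 years"; the others are a baseline SVC floor of 60% and a decline of at least 0.5 points per month. All four mirror inclusion criteria (Protocol 5.1, I 01 and I 03 to I 05). The propensity score is built from the same variables, and the balance check covers only those baseline variables.

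The endpoints include "Combined assessment of function and survival (CAFS) score at Week 52, Week 76, and Week 104", analyzed with models similar to those of SAP 3.2.2 and 3.3.1.2. CAFS uses the mITT population (SAP 3.1). Entry requires a death, or a baseline and one later ALSFRS-R (SAP 2), so there is no minimum follow-up. On unequal follow-up, SAP 3.2.1 says: "If a participant discontinues early, comparison to each other participant uses time to death if the comparator died". Failing a death, the pair is decided at the last ALSFRS-R time point that both have.

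The SAR443820 arm is planned to be followed to Week 106, and vital status is sought for participants lost to follow-up (Protocol 7.4). Protocol 9.4.5 named one Phase 3 trial as a possible control. The SAP widens this to a database, and neither document gives a historical follow-up length.

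**The concern.** The filter is said to match duration, yet no item limits how long a control was observed. Matching cannot repair this, because follow-up is not a matching variable, and the balance table would not reveal it. SAP 3.4.2 plans no sensitivity analyses for tertiary endpoints.

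Inside the randomized trial, both arms share one schedule, so late deaths are seen equally in each. Against controls from shorter trials, late deaths are visible on one side only. The pair rule does not require a death to fall within the other participant's follow-up, so the imbalance goes straight into the score. At stake is a misleading negative result, and lost power, in an analysis meant to support long-term superiority.

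**Working it through.** The plan states no power or error rate for this comparison, so there is no figure to reproduce. The sample size of 261 (261 × 2/3 = 174 on SAR443820) concerns the randomized ALSFRS-R comparison, and its placebo change and SD are redacted.

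**Inputs from the documents.** 174 SAR443820 participants matched 1:1 (SAP 3.4.3); pair rule (SAP 3.2.1); Wilcoxon-Mann-Whitney test (SAP 3.2.2); two-sided p-values (SAP 3.1), taken here at 5%.

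**Assumptions.** No true difference; event risk by Week 104 of 20% or 40% with constant hazard; SAR443820 arm followed to Week 104; all controls followed to Week L.

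**Step 1, one pair.** A SAR443820 participant dies at Week 80; the control was last seen alive at Week 52. The control wins. Swap the outcomes: a control death at Week 80 is not recorded, so a surviving SAR443820 participant gets no win from it, and the pair goes to ALSFRS-R at the last common visit.

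**Step 2, how many such pairs.** With S(t) the survival to week t, S(t) = S(104)^(t/104), and the share is q = S(L) × [S(L) − S(104)]. For L = 52:
- 20% risk: S(52) = √0.80 = 0.894; q = 0.894 × (0.894 − 0.800) = 0.084.
- 40% risk: S(52) = √0.60 = 0.775; q = 0.775 × (0.775 − 0.600) = 0.136.

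**Step 3, effect on the score.** If death is unrelated to progression, these pairs should split evenly. All go to the control, so the SAR443820 win probability is about 0.5 − q/2: 0.458 or 0.432.

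**Step 4, effect on the test.** The null SE of the win probability is √[(2n + 1)/(12n²)] = √[349/(12 × 30,276)] = 0.0310. The chance of a significant result against SAR443820 is about Φ(shortfall/0.0310 − 1.96):
- 20% risk: Φ(0.042/0.0310 − 1.96) = Φ(−0.61) = 27%.
- 40% risk: Φ(0.068/0.0310 − 1.96) = Φ(0.23) = 59%.

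**Step 5, simulation.** 1,000 runs per scenario, 174 v 174, log-normal ALSFRS-R slope with median 1 point per month, and death either unrelated to progression or linked to it (log-hazard rising by 1 per SD of progression). Ranges span both risks and both death models, for an equal drug at Week 104:

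| Controls followed to | SAR443820 win probability | Significant against SAR443820 |
|---|---|---|
| Week 26 | 0.376–0.458 | 29%–98.5% |
| Week 52 | 0.431–0.476 | 11%–61% |
| Week 76 | 0.468–0.487 | 7%–16% |
| Week 104 | 0.498–0.499 | 2.0%–3.2% |

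In the Week 52 row, the unlinked results are 28.6% and 60.8%, close to the hand calculation. The linked results are 11.4% and 21.3%: linkage shrinks the bias but does not remove it. With 20% dropout in both arms and linkage, the win probability is still 0.470–0.481.

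**Mixed pools.** A second simulation (300 replicates; slope −1.0, SD 0.6; mortality 25% or 40%) gave 8.0% or 14.7% against SAR443820 when half the controls ended at Week 52, and 28.7% or 47.3% when all did.

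**Other time points.** At Week 76, controls ending at Week 52 gave 5%–20% against SAR443820; those followed to Week 76 gave 2.0%–2.5%. At Week 52 (40% risk, linked), controls ending at Week 26 gave 13.6%; those followed to Week 52 gave 2.6%.

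**Reverse case.** With the SAR443820 arm ending at Week 52 and controls at Week 104 (linked), the win probability was 0.519–0.532, and an equal drug was found significantly better in 8.1% (20% risk) or 16.5% (40% risk) of runs.

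The simulations used no matching and no replacement, so they show mechanism and rough size, not the operating characteristics of the SAP procedure.

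**The case against.** **No historical follow-up is given.** A reader might infer that the Week 104 error rate simply is well above its nominal level. The documents do not support that: if every source trial planned 104 weeks, the bias is zero. This objection stands, and the size is conditional.

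**The pair rule is ambiguous.** Its sentence concerns someone who discontinues early, and a control who completed a 52-week trial did not. SAP 3.4.3 also asks only for similar models. Scoring over common follow-up would remove the bias. But the SAP does not state that reading, and its only sentence on unequal follow-up sets no such limit.

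**The word duration may mean disease duration**, the term used in I 03. A reader might infer a plain self-contradiction; that is not certain. Follow-up is unrestricted on either reading.

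**The direction is not fixed.** A reader might infer that the comparison must disadvantage SAR443820. Part B dosing was paused on 5 December 2023 and continued visits are only encouraged. If follow-up of the SAR443820 arm ends first, the bias reverses; vital-status collection mitigates this without guaranteeing against it. First randomization was on 28 April 2022, 586 days (83.7 weeks) before the pause, so nobody had 104 weeks of drug by then.

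**Mortality.** Protocol 2.2 says: "Most patients with ALS die from respiratory failure within 3 to 5 years after disease onset". It is tempting to conclude that most deaths fall in the unseen window. Two years since onset is an eligibility ceiling, though: someone enrolled at 6 months reaches only 2.5 years at Week 104. Mortality therefore remains an assumption.

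**Importance.** The comparison is tertiary, outside the testing hierarchy (SAP 3.5), and cannot affect the success criterion (Protocol 9.1). While the SAR443820 arm is followed longer, false findings in its favor become rarer. A reader might infer a risk of a false efficacy claim; that applies only in the reverse case.

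**Conclusion.** The gap is real and its consequence conditional. Nothing in SAP 3.4.3 restricts control follow-up, and the literal pair rule then counts late deaths on one side only. CAFS at a given time point is biased against SAR443820 by controls whose planned follow-up was shorter than that time point: under 52 weeks for Week 52, under 76 for Week 76, under 104 for Week 104.

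If all controls ended at Week 52 and 104-week mortality were 20% to 40%, an equal drug would be found significantly worse at Week 104 in very roughly 10% to 60% of analyses, against 2.5%. This is an illustration, not an estimate for this trial, and a mixed pool gives less. The practical effect is mainly lost power and a misleading negative result in a tertiary analysis. The Cox and MMRM comparisons in the same section treat short follow-up as censoring or missing data, so they do not share this mechanism.

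**What to change.** In SAP 3.4.3, state that each external-control CAFS pair, deaths included, is scored only up to the earlier of the two participants' planned end of follow-up. State also what counts as the planned end for the SAR443820 arm if its follow-up is closed early, so that the rule covers the reverse case. In the linked simulation without dropout, with controls ending at Week 52 or 76, counting deaths only within common follow-up gave a win probability of 0.497 and total two-sided rejection of 4.3% to 5.3%.

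Alternatively, where the planned length of the source trial is recorded, use for each CAFS time point only controls from trials planned to last at least that long. With 104-week controls, total rejection was 3.3% to 5.1%. The filter must use planned, not observed, follow-up. Requiring controls to have been observed for 104 weeks removes control deaths and gave win probabilities of about 0.40 (20% risk) or 0.30 (40% risk), with significant results against an equal drug in 91% to 100% of 400 runs.

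The scoring rule costs SAP wording and some late information. The filter costs a smaller control pool and re-matching by time point, and the documents do not say whether planned trial length is available in the database.

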3.2.2 Main analytical approach

Part A

The primary endpoint in Part A will be analyzed with the estimand defined according to the following attributes:

- Endpoint: Change from baseline in the ALSFRS-R total score to Week 24
- Treatment condition: SAR443820 will be compared to placebo
- Analysis population: ITT population
- Intercurrent events (IE):
 - The IMP discontinuation IE will be handled with the treatment policy strategy; The primary endpoint will be assessed based on all assessments irrespective of the IMP discontinuation
- Population-level summary: The primary endpoint will be analyzed using MMRM with change from baseline in ALSFRS-R total score up to Week 24 as response variable, and treatment, visit, randomization strata of the geographic region of the study site, ALS onset region (bulbar or other areas), use of riluzole (yes or no), use of edaravone (yes or no), use of the combination of sodium phenylbutyrate and taurursodiol (yes or no), treatment-by-visit interaction, disease duration (from first symptom onset to the screening visit), baseline ALSFRS-R score, baseline NfL, disease duration-by-visit interaction, baseline NfL-by-visit interaction and baseline ALSFRS-R score-by-visit interaction as covariates. If less than 10 participants in a randomization strata level, then the corresponding factor will not be included as a covariate in the MMRM model.

The least squares mean difference in the ALSFRS-R change from baseline at Week 24 between SAR443820 vs placebo, together with the p-value and the 95% CI for the difference, will be estimated from the MMRM model using weights for each stratum equal to the overall proportion of participants in each stratum (ie, “population weight”) by inclusion of the OBSMARGINS option in the LSMEANS statement. Plots of least squares means (\pm standard error) over time will be provided.

This model will be implemented using the SAS MIXED procedure with an unstructured covariance matrix to model the within-participant errors. Parameters will be estimated using the restricted maximum likelihood method. The denominator degrees of freedom will be estimated using the Kenward-Roger approximation. This model will provide baseline adjusted least-squares means estimates at Week 24 for SAR443820 and placebo, together with their corresponding standard errors and CIs. If this model fails to converge, the following variance-covariance structures will be tested in this order:

- Heterogeneous Toeplitz
- Heterogeneous AR(1)

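### External-control match (SAP 3.4.3): ALS onset region and riluzole use are not among the named matching variables, which leaves the unadjusted CAFS comparison exposed

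*SAP*

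**What the plan says.** SAP 3.4.3 gives the purpose of the match: "Propensity score matching seeks to balance the distributions of known prognostic covariates in treatment and control group". Step 1 filters the historical database on four items: "Age 18 – 80 years, inclusive"; "First ALS symptom onset" no more than 2 years ago; baseline SVC at least 60%; and "Baseline ALSFRS-R decline rate" at least 0.5 per month. Step 2 then says: "A logistic regression for the treatment group as the dependent variable is performed to obtain the propensity score with the abovementioned matching variables". No other list of matching variables is given. Matching is 1:1, by Mahalanobis distance, with replacement. The text does not say whether the distance is computed on the score, on the covariates or on both. Balance before and after matching is summarized for the matching variables only, with no criterion for adequate balance.

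The matched groups are then compared "using the similar analyses models as described for the primary and secondary endpoints in" SAP 3.2.2 and 3.3.1.2. The MMRM in 3.2.2 contains the randomization strata (including onset region and riluzole use), disease duration and, in the SAP's words, "baseline ALSFRS-R score, baseline NfL, disease duration-by-visit interaction, baseline NfL-by-visit interaction". The Cox model in 3.3.1.2 contains the same strata, disease duration, baseline ALSFRS-R and baseline NfL. CAFS is tested by Wilcoxon-Mann-Whitney with no covariates (3.2.2, carried over by 3.3.1.2).

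**The concern.** In the randomized comparison, onset region and riluzole use are balanced by stratified randomization. A historical control loses that protection, and the match is meant to replace it. A match built on the four named variables does nothing direct about these two factors, although the SAP treats both as prognostic in its own models. The balance table would not show the gap either, because it covers only variables already in the match.

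The point matters most for CAFS, which heads the list of endpoints in 3.4.3. CAFS ranks on survival first, and Protocol 2.2 credits riluzole with a moderate effect on survival. A difference in riluzole use between the groups could therefore enter the ranks with nothing in the planned test to remove it. SAP 3.4.3 states that the aim is to demonstrate superiority.

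**Working it through.** **1. The plan's own figure.** SAP 3.4.3 plans to match 174 SAR443820 participants. From 261 randomized 2:1, 261 × 2/3 = 174, which reproduces.

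**2. Covariate lists side by side.**

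| Factor | Stratum (SAP 1.1) | MMRM (3.2.2) | Cox (3.3.1.2) | Named in 3.4.3 |
|---|---|---|---|---|
| ALS onset region | yes | yes | yes | no |
| Riluzole use | yes | yes | yes | no |
| Edaravone; phenylbutyrate/taurursodiol | yes | yes | yes | no |
| Geographic region | yes | yes | yes | no |
| Baseline NfL | no | yes | yes | no |
| Baseline ALSFRS-R | no | yes | yes | not by name (see 3) |
| Disease duration | no | yes | yes | yes |
| Age, SVC, decline rate | no | no | no | yes |

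**3. Baseline ALSFRS-R.** SAP 5.3 and Protocol criterion I 04 define pre-study slope as (48 − screening ALSFRS-R)/months since onset. Hence screening ALSFRS-R = 48 − slope × duration:
- 48 − 0.5 × 24 = 36
- 48 − 1.0 × 12 = 36
- 48 − 1.0 × 18 = 30

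Matching on slope and duration as continuous variables therefore largely fixes the screening score.

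**4. Form of the variables.** Read as pass/fail indicators, the four filters are constant after filtering. Every SAR443820 participant meets them by eligibility and every retained control meets them by selection. They can enter a propensity model only as continuous values, which the SAP does not say.

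**5. What a four-variable match does to a factor unrelated to those four.** The documents give no prevalences, so these are assumed: bulbar onset 20% (treated) vs 30% (historical), and riluzole use 80% vs 60%. Standardised difference = difference in proportions / √(mean of the two variances):
- Bulbar: −0.10 / √[(0.20 × 0.80 + 0.30 × 0.70)/2] = −0.10/0.430 = −0.23
- Riluzole: 0.20 / √[(0.80 × 0.20 + 0.60 × 0.40)/2] = 0.20/0.447 = 0.45

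A simulation used 174 treated, 1,500 controls, 60 replicates and modest assumed shifts in the four variables. Onset region and riluzole use were drawn independently of those four, and ALSFRS-R was set to 48 − slope × duration. Standardised differences:

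| | Bulbar | Riluzole | ALSFRS-R |
|---|---|---|---|
| Before matching | −0.23 | 0.45 | 0.24 |
| Four variables, propensity score | −0.23 | 0.44 | −0.01 |
| Four variables, Mahalanobis | −0.23 | 0.46 | 0.00 |
| Plus onset, riluzole, ALSFRS-R: propensity score | −0.01 | 0.00 | −0.01 |
| Plus onset, riluzole, ALSFRS-R: Mahalanobis | 0.00 | 0.00 | 0.01 |

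After four-variable matching about 10 percentage points of imbalance in bulbar onset and about 20 in riluzole use remain. The within-pair correlation of ALSFRS-R was 0.97 with Mahalanobis distance on the four variables and 0.36 with the propensity score alone, so the unstated distance variables affect how close the pairs are.

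**6. Which endpoint is exposed.** ALSFRS-R change and the time-to-event endpoints go to models similar to ones that contain onset region and riluzole use. CAFS goes to a rank test with none. SAP 3.3.1.3 describes a rank-ANCOVA sensitivity analysis for CAFS, but 3.4.3 carries over only 3.2.2 and 3.3.1.2, and 3.4.2 rules out sensitivity analyses for tertiary endpoints.

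**The case against.** Three stronger readings are tempting, and the documents do not support them.

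- A reader might infer that baseline ALSFRS-R is left unmatched. Step 3 shows otherwise. The remaining gaps are drift between screening and Day 1, a different slope definition in the historical database, or loose pairing under a score-only match. These justify a line in the balance table, not a claim of omission.
- A reader might multiply an assumed 10–20 point prevalence gap by an assumed 2–4 point prognostic difference and report a bias of 0.2–0.8 ALSFRS-R points (0.10 × 2 = 0.2; 0.20 × 4 = 0.8). That describes an unadjusted ALSFRS-R comparison, which the SAP does not plan. It does not carry over to CAFS, which is a rank score.
- A reader might state flatly that the score uses only these four variables. That is the natural reading, but the SAP calls them filtering factors and never defines its matching variables. What is certain is that the list is undefined and nothing else is named.

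The best defence is that regression after matching covers what the match omits, that a rank-ANCOVA for CAFS exists in the SAP, and that the historical database may not record the extra factors. The first part stands for MMRM and Cox, subject to the word similar, which does not fix the covariates. The second stands only partly: the analysis is not extended to this comparison, and the content of SAP 3.2.3, to which it refers, is not shown in the public copy. The third is open, because the database is given only as an example and Protocol 9.4.5 names a different source, a Phase 3 ceftriaxone trial. If onset region and riluzole use are unavailable, the models cannot adjust for them either, and the SAP should say so.

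The stakes are also limited. Protocol 9.4.5 says only that the analysis might be done, and the pause of Part B dosing already complicates any comparison over 104 weeks of treatment.

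**Conclusion.** The point holds in a limited form. SAP 3.4.3 names no matching variables beyond the four filters and leaves the distance variables unstated. Onset region and riluzole use are therefore not matched on the visible text, and the planned balance check would miss an imbalance in them. The exposed comparison is CAFS at Weeks 52, 76 and 104.

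No size or direction of bias can be derived. The simulation shows only that a four-variable match leaves unrelated factors as imbalanced as it found them. Its prevalences and the independence of the factors are assumptions, and correlation with the four variables would change the result. The conclusion on ALSFRS-R change and survival assumes that the post-match models keep onset region and riluzole use as covariates.

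This is a minor point. The analysis is tertiary, lies outside the hierarchy in SAP 3.5, and does not bear on the Part A conclusion.

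**What to change.** Amend SAP 3.4.3 as follows:

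- List the propensity-score variables and the Mahalanobis variables explicitly: age, symptom duration, SVC and decline rate as continuous values, plus ALS onset region and riluzole use. Add baseline NfL and other background therapy where the chosen database records them, and state which of these are unavailable.
- Report standardised differences before and after matching for every available outcome-model covariate, including baseline ALSFRS-R, whether or not it is in the match.
- Add a covariate-adjusted rank analysis of CAFS at Weeks 52, 76 and 104 for this comparison, as an exception to the rule in 3.4.2.

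The cost is a few lines of SAP text and some looser matches. In the simulation with the three added variables, the Mahalanobis match moved the standardised difference for SVC from 0.02 to 0.04 and for age from −0.02 to −0.03. Under score-only matching the within-pair correlation of ALSFRS-R fell from 0.36 to 0.17.
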